4. STUDY DESIGN

4.1 Overall Study Design

This is a double-blind, dose escalating, randomized, vehicle-controlled study designed to assess the efficacy and safety of patidegib gel 2% and 4% in comparison with vehicle applied once or twice daily. The population of subjects will be enrolled from the **PPD**

Approximately 36 subjects who meet the study entry criteria will be randomized to one of four sequential cohorts. Each cohort will have 6 subjects randomized to active drug and 3 randomized to vehicle. The four sequential cohorts will be:

- Cohort 1: patidegib gel 2% or vehicle applied once daily,
- Cohort 2: patidegib gel 4% or vehicle applied once daily,
- Cohort 3: patidegib gel 2% or vehicle applied twice daily, and
- Cohort 4: patidegib gel 4% or vehicle applied twice daily.

As soon as one cohort has been enrolled the next cohort will be recruited. The study drug will be applied topically to the treatment-targeted nodular BCCs once or twice daily for 12 weeks of treatment.

Upon completion of the 12-week treatment period, all subjects will be asked to return to the investigational center for final evaluation. At the Week 12 visit the treatment site(s) will be excised. The area excised should at a minimum include the original diameter of the tumor. This means that if the tumor has shrunk in size the entire original area of the BCC will be excised, not just the visually apparent residual tumor. During the study, subjects will be allowed to use moisturizers and emollients and sunscreen. The Investigator will assess the areas affected at each visit.

The treatment-targeted BCC(s) will be identified by the Investigator at the Baseline visit and will be circled in ink at Baseline, Weeks 6 and 12, and photographed, and measured at all study visits (Baseline, Weeks 2, 6, 8, 10, and 12).

Biomarkers: On each subject one or two baseline previously untreated nodular BCCs designated as a treatment-targeted tumor will be biopsied and at the end of 12 weeks of treatment the treatment site(s) will be excised. Both samples will be evaluated histologically and for determination of GLI1 mRNA levels.

Blood samples for complete blood count and serum chemistry and urine for urinalysis will be collected from subjects at Screening, Week 6, and Week 12.

Subjects who terminate study participation early will be asked to complete all Week 12 assessments, as appropriate, prior to commencement of any alternative therapy for BCC (if possible). Subjects who discontinue from the study during the treatment period will not be replaced.

If signs or symptoms develop in the treatment areas during the treatment period that restrict daily activities or make continued application of the study drug difficult due to discomfort, the Investigator may instruct the subject to interrupt use of the study drug temporarily and to resume application of the study drug once the signs/symptoms have subsided. The Investigator should try to minimize study drug interruptions; and if needed, make best efforts to limit a "drug holiday" to no more than 7 days. If the study drug interruption does exceed 4 consecutive days, the Investigator should consult with the Medical Monitor to determine a course of action. If the study drug is interrupted, discontinued, or a concomitant medication is used to treat a sign or symptom, an AE shall be recorded.

Subjects who discontinue participation in the study due to clinically significant laboratory abnormalities or AEs will be asked to complete all Week 12 evaluations. Any subject who has an AE during the treatment period will be monitored by the Investigator until resolution (return to normal or to the baseline state) or stabilization, as determined by the Investigator.

In addition, application of study drug may be delayed or halted at any time if ongoing safety data evaluations raise concern for subject safety. If the subject participation is suspended, all of the subject's safety data will be reviewed by the Medical Monitor in conjunction with the Investigator to determine course of action.

4.1.1 Schedule of Visits and Assessments

The schedule of assessments can be found in Section 5.1 of the protocol.

4.1.2 Method of Assigning Subjects to Treatment Groups

This is a double-blinded study, in which the identity of the study drug will be unknown to Investigator and subjects, as well as to all individuals closely associated with the study.

Subjects will be enrolled into 1 of the 4 sequential study drug groups of 9 subjects with 6 being randomized to active and 3 to vehicle within each group. The sequential groups will be patidegib or vehicle gel 2% applied once daily, patidegib or vehicle gel 4% applied once daily, patidegib or vehicle gel 4% applied twice daily. Each screened subject will be assigned a unique 5-digit study subject number assigned by the investigational center, which will consist of the 2 digit investigational center number and the 3 digit chronological screening order number, starting with 001 (e.g., 01001, 01002). The study

drug kit will be assigned to subjects based on a randomization code, and kits will be dispensed to the subjects at Baseline in the order that they are enrolled by taking the lowest numbered kit available in inventory at the investigational site. A study drug accountability log will document the inventory and dispensing of study drug at the investigational center.

4.1.3 Blinding

The study drugs will be packaged and labeled identically, and the study drug kits will be numbered sequentially and dispensed randomly to the subjects on the study. Study drug supplies will be distributed to the investigational center to maintain the randomization ratio.

As a double-blinded study, the Investigators, the site staff, PellePharm, and the Clinical Monitor(s) will not be aware of the treatment assigned to the individual study subjects. Delegated staff members at the investigational center will dispense the study drugs and will collect and weigh all used and unused study drug tubes as scheduled.

The treatment assignments for all enrolled subjects will be completely unblinded only after the conclusion of the treatment phase of the study. However, after Cohorts 1 and 2 have complete biopsy results, and again after Cohort 3 has complete biopsy results, the sponsor and the CRO will be unblinded in order to assess limited safety and efficacy results.

5. EFFICACY AND SAFETY ENDPOINTS

5.1 Efficacy Endpoints

The efficacy endpoints are intended to compare once and twice daily application of 2% patidegib gel, 4% patidegib gel, and vehicle gel. Efficacy assessments will be summarized descriptively by treatment group and visit. P-values will be provided for descriptive purposes only.

5.1.1 Primary Efficacy Endpoint

The primary efficacy endpoint is change in GLI1 mRNA levels in drug-treated versus vehicle-treated tumors at Week 12.

5.1.2 Secondary Efficacy Endpoint

The secondary efficacy endpoint is the decrease in tumor size defined in two ways:

1. Percent of baseline treatment targeted BCCs with Complete or Partial Response at Week 12 as assessed by blinded photographic review where Complete Response is determined when there is no longer any visible evidence of a lesion consistent with BCC at the site, Partial Response is determined when although a BCC still remains at this site, it has demonstrated a visible decrease in size compared with baseline, and No Response is

determined when the BCC has not demonstrated any visible decrease in size compared with baseline, and;

2. Percent decrease in the greatest diameter of baseline treatment targeted BCCs at Week 12.

5.1.3 Exploratory Efficacy Endpoints

The first exploratory endpoint is the proportion of baseline treatment-targeted BCCs that are evaluated as being clear or almost clear in the investigator static global tumor assessment (ISGTA) assessment.

The second exploratory endpoint is the proportion of baseline treated tumors that are smaller based on blinded photographic review. Tumor area will also be assessed at each study visit. From tumor area, a 'Yes/No' for whether the tumor is smaller will be derived such that if area at visit is less than area at baseline this is 'Yes'.

5.2 Safety Endpoints

Safety will be assessed through adverse events, dermal safety and tolerability, safety laboratory values and vital signs measurements, and pregnancy tests.

6. STATISTICAL AND ANALYTICAL PLANS

6.1 General Methodology

All statistical processing will be performed using Statistical Analysis System (SAS®) unless otherwise stated. No interim analyses are planned. If determined appropriate by the Sponsor, limited safety and efficacy interim analysis on tumor shrinkage and biomarkers may be performed.

Formal inferential testing will not be performed, however p-values will be provided for descriptive purposes. Descriptive statistics will be used to provide an overview of the efficacy and safety results. P-values which are supplied are for descriptive purposes only. For categorical parameters, the number and percentage of subjects in each category will be presented. For continuous parameters, descriptive statistics will include n (number of subjects), mean, standard deviation (SD), median, minimum (min), and maximum (max). For by treatment group summaries the vehicle gel group from each cohort will be combined into a single group.

The last observation carried forward method (LOCF) will be used to impute missing secondary and exploratory efficacy data (i.e., the last available on-therapy observation for a subject will be used to estimate subsequent missing data points). Analyses will also be carried out on an 'as

observed' basis without imputation. No imputations will be made for missing primary endpoint data or safety data.

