10. STATISTICS

All statistical processing will be performed using SAS[®] unless otherwise stated. If determined appropriate by the Sponsor, limited safety and efficacy interim analysis on tumor shrinkage and biomarkers may be performed.

No inferential testing will be performed. Descriptive statistics will be used to provide an overview of the efficacy and safety results. For categorical parameters, the number and percentage of subjects in each category will be presented. For continuous parameters, descriptive statistics will include n (number of subjects), mean, and standard deviation, median, minimum, and maximum.

No imputation will be made for the primary endpoint. For the secondary endpoint, the last observation carried forward method (LOCF) will be used to impute missing efficacy data (i.e., the last available on-therapy observation for a subject will be used to estimate subsequent missing data points). No imputations will be made for missing safety data.

A statistical analysis plan (SAP), describing all statistical analyses will be provided as a separate document. The SAP will be finalized prior to unblinding of the study treatments.

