10.7 Assessment of Efficacy

10.7.1 Efficacy Summaries

The efficacy endpoints are intended to compare once and twice daily application of 2% patidegib gel, 4% patidegib gel, and vehicle gel. Efficacy assessments will be summarized descriptively by treatment group and visit.

10.7.1.1 Primary Efficacy Endpoint:

Change in GLI1 mRNA levels in drug-treated versus vehicle-treated tumors after 12 weeks of treatment.

10.7.1.2 Secondary Efficacy Endpoints:

The secondary efficacy endpoint is the decrease in tumor size defined as percent decrease in the greatest diameter of baseline treatment targeted BCCs at the Week 12.

10.7.1.3 Exploratory Efficacy Endpoints:

To evaluate the utility of an investigator static global tumor assessment (ISGTA) in assessing the proportion of baseline treatment-targeted BCCs that are evaluated as being clear or almost clear.

To evaluate if the proportion of baseline treated tumors are smaller based on photographic review

10.7.2 Efficacy Analyses.

The primary endpoint and the secondary endpoints of change in tumor size, and reduction in the HH signaling pathway will be evaluated with an analysis of covariance (ANCOVA) with treatment group as a factor and baseline value as a covariate. Pairwise comparisons will be performed using contrasts within the ANCOVA. Additionally, t-tests for pairwise comparisons of the primary endpoint will be done, or alternatively a non-parametric approach may be used.

The exploratory analysis of ISGTA will be analyzed with a Cochran-Mantel-Haenszel test

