6.1.8 Multiple Comparisons/Multiplicity

Not applicable. Inferential tests will not be performed.

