6.7.1 Primary Efficacy Analysis

The primary endpoint of change in GLI1 mRNA levels will be evaluated with an analysis of covariance (ANCOVA) with treatment group as factor and baseline value as covariate. Analysis is on a by tumor level. Pairwise comparisons as well as any treated (combining all patidegib groups) versus vehicle will be performed using contrasts within the ANCOVA.

Additionally, if number of results is sufficient, a t-test will be done to perform pairwise comparisons of change in GLI1 mRNA levels of each treatment group with vehicle (and combined patidegib versus vehicle). If assumptions required for a t-test are not met, then a Mann Whitney U test will be performed.

Data will be summarized by visit. Both change from baseline and percent change from baseline will be presented.

This analysis will be done for 2 regions (1) BCC and (2) BCC + tumor-associated stroma.

No imputation on GLI1 data will be performed.

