Min. to Max.	xx to xx	xx to xx	xx to xx	xx to xx	xx to xx
At least 40% Decrease from Baseline	xx (xx.x%)	xx (xx.x%)	xx (xx.x%)	xx (xx.x%)	xx (xx.x%)

P-value versus Vehicle Gel ^b	X.XXX	X.XXX	X.XXX	X.XXX	
P-value versus Patidegib Gel 2% QD ^b		X.XXX	X.XXX	X.XXX	
P-value versus Patidegib Gel 2% BID ^b			X.XXX	X.XXX	
P-value versus Patidegib Gel 4% QD ^b				X.XXX	
P-value All Patidegib vs Vehicle Gel					X.XXX
P-value versus Vehicle Gel ^c	X.XXX	X.XXX	X.XXX	X,XXX	
P-value versus Patidegib Gel 2% QD ^c		X.XXX	X.XXX	X.XXX	
P-value versus Patidegib Gel 2% BID ^c			X.XXX	X,XXX	
P-value versus Patidegib Gel 4% QD ^c				X.XXX	
P-value All Patidegib vs Vehicle Gel					X.XXX

Repeat Above for 1:BCC + tumor-associated stroma region H-Score

Note: Missing values are not imputed; all available data is summarized.

SOURCE: USERNAME\SPONSOR\PROJECT\JOBNAME (DATE,TIME)

^a Change from Baseline calculated as (Week 12 – Baseline). Percent Change from Baseline calculated as (Week 12 - Baseline) / Baseline * 100. ^b P-value of pairwise comparison using ANCOVA with a factor of treatment group and using Baseline value as a covariate.

^c P-value of pairwise comparison using t-test (or Mann Whitney U if the case).

Table 14.2.2.1.1: Analysis of the Secondary Efficacy Endpoint: Proportion of CR/PR Response at Week 12 (Intent-to-Treat Population)

	Patidegib Gel 2% QD (N=xx)	Patidegib Gel 2% BID (N=xx)	Patidegib Gel 4% QD (N=xx)	Patidegib Gel 4% BID (N=xx)	Vehicle Gel (N=xx)
Proportion of CR/PR Response at					
Week 12 ^a					
Number of tumors	XX	XX	XX	XX	XX
CR / PR	XX.X	XX.X	XX.X	XX.X	XX.X
Non Response	XX.XX	XX.XX	XX.XX	XX.XX	XX.XX
P-value versus Vehicle Gel ^c	x.xxx	x.xxx	x.xxx	X.XXX	
P-value versus Patidegib Gel 2% QD ^c		X.XXX	X.XXX	X.XXX	
P-value versus Patidegib Gel 2% BID ^c			X.XXX	X.XXX	
P-value versus Patidegib Gel 4% QD ^c				X.XXX	
P-value All Patidegib vs Vehicle Gel					x.xxx

Note: Missing values are not imputed.

SOURCE: USERNAME\SPONSOR\PROJECT\JOBNAME (DATE,TIME)

Table 14.2.2.1.2: Analysis of the Secondary Efficacy Endpoint: Proportion of CR/PR Response at Week 12 (Per Protocol Population)

As assessed by blinded photographic review.
 P-value of pairwise comparison using 2-sided Fisher's Exact test.

Table 14.2.2.2.1: Analysis of the Secondary Efficacy Endpoint: Percent Decrease in Baseline Treatment Targeted Tumor Size at Week 12 (LOCF) (Intent-to-Treat Population)

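### The only planned comparison between groups is a p-value: about 386 of them by shell count, with no multiplicity adjustment and no difference or confidence interval

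*SAP*

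**What the plan says.** Three statements disclaim inference.

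- Protocol section 10: "No inferential testing will be performed. Descriptive statistics will be used to provide an overview of the efficacy and safety results". Protocol 10.8.7 repeats this under multiplicity.
- SAP 6.1: "Formal inferential testing will not be performed, however p-values will be provided for descriptive purposes".
- SAP 6.1.8, on multiplicity: "Not applicable. Inferential tests will not be performed".

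The analysis sections then plan tests. Protocol 10.7.2 says: "Pairwise comparisons will be performed using contrasts within the ANCOVA". SAP 6.7.1 says of GLI1: "Pairwise comparisons as well as any treated (combining all patidegib groups) versus vehicle will be performed using contrasts within the ANCOVA". It adds t-tests or Mann-Whitney U tests. SAP 6.7.2 adds Fisher's exact tests for photographic response and treats diameter like GLI1. SAP 6.7.3 adds Cochran-Mantel-Haenszel (CMH) tests for ISGTA and for the smaller/not-smaller outcome, and an ANCOVA for tumor area.

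For reporting, SAP 6.1 says: "For continuous parameters, descriptive statistics will include n (number of subjects), mean, standard deviation (SD), median, minimum (min), and maximum (max"). It also says: "For by treatment group summaries the vehicle gel group from each cohort will be combined into a single group". The tables therefore have five columns. In the visible efficacy shells (Tables 14.2.1.1 to 14.2.4.1) the per-arm summaries are followed by p-value rows. A footnote to Table 14.2.1.1 describes one block as: "P-value of pairwise comparison using ANCOVA with a factor of treatment group and using Baseline value as a covariate". No visible shell, and no methods text, asks for an adjusted mean, a treatment difference, a standard error of a difference, an odds ratio or a confidence interval.

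**The concern.** SAP section 2 gives the goal as establishing a dose and regimen for later trials. That decision needs the estimated difference between each regimen and vehicle, the differences between regimens, and how uncertain they are. A p-value gives neither. The ANCOVA that would supply the estimates is fitted, but only its p-values reach the tables.

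With six subjects per regimen, a large p-value between two regimens says little, yet without an interval beside it, it is easily read as evidence of no difference. A small one among several hundred unadjusted results is as easily over-read. Calling the p-values descriptive does not prevent either, and the disclaimer is the plan's only reason for not addressing multiplicity.

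**Working it through.** The documents state no p-value count, alpha, power, effect size or SD (SAP section 7 says only that this is a dose-ranging study), so there is no planned figure to reproduce.

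**Count of planned p-values, from the shells.** Five columns give 5 × 4 / 2 = 10 pairwise contrasts. All patidegib against vehicle makes 11 per set, except for ISGTA, whose shell shows only the 10. SAP 6.7 requires each analysis in two populations (ITT and PP).

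| Endpoint | Calculation | p-values |
|---|---|---|
| GLI1 | 11 × 2 tests × 2 regions × 2 populations | 88 |
| Photographic response | 11 × 1 test × 2 populations | 22 |
| Diameter | 11 × 2 tests × 2 (LOCF, as observed) × 2 populations | 88 |
| ISGTA | 10 × 5 visits × 2 populations | 100 |
| Tumor area and smaller/not smaller | 11 × 2 tests × 2 time points × 2 populations | 88 |
| Total | | 386 |

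Range by reading:

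- Leaving out the GLI1 PP table, whose shell is not visible: 386 − 44 = 342.
- Adding the pooled contrast to ISGTA: 386 + 10 = 396.
- Running both area tests at all five post-baseline visits, as the text of SAP 5.1.3 and 6.7.3 suggests, instead of the shell's two: area becomes 11 × 2 × 5 × 2 = 220, and the total 386 − 88 + 220 = 518.

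**Chance findings within one ANCOVA.** I simulated no effect with 6, 6, 6, 6 and 12 subjects, one tumor each, one covariate and 30 residual df (40,000 runs). The chance of at least one p < 0.05 is about 17% over the four regimen-against-vehicle contrasts and about 27% over all ten.

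**Precision that the tables would not show.** Inputs: 6 active and 3 vehicle per cohort in four cohorts (SAP 4.1), hence 6 per regimen, 12 pooled vehicle and 24 on any patidegib. Residual df = 36 − 5 − 1 = 30. Assumptions: one tumor per subject, no dropout. Half-width in residual SD units = t(0.975, 30) × √(1/n₁ + 1/n₂), with t = 2.042.

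- Regimen against vehicle: 2.042 × √(1/6 + 1/12) = 1.02 SD
- Regimen against regimen: 2.042 × √(1/6 + 1/6) = 1.18 SD
- All patidegib against vehicle: 2.042 × √(1/24 + 1/12) = 0.72 SD

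**Can a reader rebuild the missing results?** A crude difference, yes: subtract the arm means or proportions. The adjusted difference, no: it needs the fitted baseline slope, which no shell reports. A valid interval, no: the printed n counts tumors, a subject may contribute two, and the tables do not show the within-subject correlation.

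**Would the planned model give a valid interval?** Not if many subjects have two tumors, because SAP 6.1.4 lists only treatment and baseline as terms. I simulated the extreme case of two tumors in every subject for 6 against 12 subjects, treating tumors as independent and leaving out the covariate. A nominal 95% interval covers about 91%, 89% and 86% when the within-subject correlation is 0.3, 0.5 and 0.7. These correlations are assumptions; the documents give none.

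**The case against.** The fairest defense is that this is a 36-subject proof-of-concept study that makes no power claim and openly labels its p-values as descriptive. Three stronger readings are tempting, and the documents do not support them.

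- *Effect size and precision by regimen go unreported.* A reader might infer this, but the shells give each arm's number of tumors with mean, SD, median and range, or with responder counts. GLI1 has change, percent change and the proportion with at least a 40% decrease. Within-arm response and spread are reported; the between-group estimate and its interval are not.
- *SAP 6.1 contradicts itself.* It does not: the sentence that disclaims formal testing also announces the p-values, and SAP 5.1 repeats the label. The conflict is between SAP 6.1.8 and Protocol section 10 on one side and SAP 6.7 and Protocol 10.7.2 on the other.
- *About 19 false positives are to be expected* (386 × 0.05 = 19.3). This is too high. Of the 386, 22 + 100 + 44 = 166 are Fisher or CMH tests on small binary samples, whose true size is often well below 5%. At a 30% response rate in both groups, exact enumeration gives Fisher's test a size of 0.3% for 6 against 6 and 1.8% for 6 against 12. A rough expected count is 12 to 16, under assumed null rates of 20–50% for photographic response and smaller/not smaller and 2–30% for ISGTA. Many of the 386 also repeat one contrast across populations, imputation rules or tests, so they are not separate chances of error.

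Two further objections stand. The documents set no p-value threshold for choosing a regimen, so how readers will choose is a risk, not a planned rule. And removing nearly all the p-values is a preference; the need is met by placing estimates and intervals beside them.

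**Conclusion.** The point holds in this form. Tests are disclaimed in SAP 6.1.8 and Protocol section 10 but planned in SAP 6.7. P-values without multiplicity adjustment (386 by shell count, 342 to 518 depending on reading) are the only between-group output, and no difference or interval is planned. The ANCOVA p-values are adjusted for baseline; it is multiplicity that goes unaddressed.

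The statement about shells covers those visible in the public text, since the start of the table index is missing. The half-widths of 1.02, 1.18 and 0.72 SD illustrate one tumor per subject and no dropout; second tumors would narrow them and missing samples would widen them. This does not invalidate the trial. It is a cheap improvement that lets the results address the regimen question.

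**What to change.** In SAP 6.1, SAP 6.7 and the efficacy shells:

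1. For GLI1, diameter and tumor area, add the adjusted mean difference with a 95% confidence interval for each regimen against vehicle, all patidegib against vehicle, and between regimens. Take these from the planned ANCOVA extended with a subject random effect or subject-clustered standard errors, with small-sample degrees of freedom because there are only six subjects per regimen.
2. For photographic response, ISGTA success and smaller/not smaller, add differences in proportions with intervals that allow for two tumors per subject. Use exact intervals only where each subject has one tumor.
3. State that the intervals, and any p-values kept, are not adjusted for multiplicity.
4. Reword SAP 6.1.8 and Protocol sections 10 and 10.8.7 to agree with SAP 6.7 and Protocol 10.7.2.

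No new data are needed and the base models are already planned. The cost is shell and wording edits, a clustering term, and wide intervals shown openly.

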Approximately 36 subjects who meet the study entry criteria will be enrolled into one of four sequential cohorts. As soon as one cohort has been completely enrolled, the next cohort will be enrolled. Each subject will treat no more than two previously untreated biopsy confirmed treatment-targeted nodular BCCs. If the subject has additional non-treatment targeted BCCs they can be treated surgically or with topical agents prior to or during the trial. Within each cohort subjects will be randomized in a 2:1 ratio to receive active or vehicle gel. The sequential cohorts will be:

- Cohort 1: patidegib gel 2% or vehicle, once daily
- Cohort 2: patidegib gel 4% or vehicle, once daily
- Cohort 3: patidegib gel 2% or vehicle, twice daily
- Cohort 4: patidegib gel 4% or vehicle, twice daily

The study drug will be applied topically to the treatment-targeted BCCs and a rim or adjacent skin for 12 weeks.

Information on reported and observed adverse events (AEs) will be obtained at each visit. An abbreviated physical examination (PE) will be performed at Baseline and Week 12.

The treatment-targeted BCCs will be identified by the Investigator at the Baseline visit and will be circled in ink at Baseline, Weeks 6 and 12, and photographed, and measured at all study visits (Baseline, Weeks 2, 6, 8, 10, and 12).

Blood samples for complete blood count and serum chemistry and urine for urinalysis will be collected from subjects at Screening, Week 6, and Week 12.

Subjects who terminate study participation early will be asked to complete all Week 12 assessments, as appropriate, prior to commencement of any alternative therapy for BCCs (if possible). Subjects who discontinue from the study during the treatment period will not be replaced.

If signs or symptoms develop in the treatment areas during the treatment period that restrict daily activities or make continued application of the study drug difficult due to discomfort, the Investigator may instruct the subject to interrupt use of the study drug temporarily and to resume application of the study drug once the signs and symptoms have resolved adequately to the point that the Investigator believes that treatment can safely be resumed. The

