- 9. The subject has a history of invasive cancer within the past five years excluding non-melanoma skin cancer, Stage I cervical cancer, ductal carcinoma in situ of breast, or chronic lymphocytic lymphoma (CLL) (Stage 0).
- 10. The subject is currently participating in an experimental drug study, (within 4 weeks of Baseline visit), or plans to participate in an experimental drug study while enrolled in this study.
- 11. The subject is on a concomitant medication that is a strong CYP3A4 inhibitor. These include, but are not limited to: larithromycin, telithromycin, nefazodone, itraconazole, ketoconazole, atazanavir, darunavir, indinavir, lopinavir, nelfinavir, ritonavir, saquinavir, and tipranavir.

Investigational Product, Reference Therapy, Dosage and Mode of Administration:

- patidegib gel 2%, applied topically, once daily for 12 weeks
- patidegib gel 4%, applied topically, once daily for 12 weeks
- patidegib gel 2%, applied topically, twice daily for 12 weeks
- patidegib gel 4%, applied topically, twice daily for 12 weeks
- vehicle gel, applied topically, once daily for 12 weeks
- vehicle gel, applied topically, twice daily for 12 weeks

Application Instructions:

The Investigator or their designee will instruct the subject on how to apply the study drug to the previously biopsied treatment-targeted BCCs identified at the Baseline visit by the Investigator. The staff member will instruct the subject on the proper application procedure during the Baseline visit. The quantity of gel to be applied will be defined using laminated dosing cards. Approximately 20 mg of gel will be applied to each tumor at each treatment. The subject is to treat no more than two treatment-targeted BCCs. If the subject has additional BCCs they may be treated surgically or topically during the trial. In addition to the verbal instructions given during the visit, the subjects will be provided with written instructions for proper application technique.

Because sunlight can increase the development of skin cancers subjects will be advised to avoid or minimize exposure to direct sunlight while in the study. Subjects will also be advised to wash their hands before and after application of the study drug.

The amount of study drug used by the subjects will be guided by instructing the subjects to use dosing cards that will provided to them, and monitored by weighing each newly dispensed study drug tube, and re-weighing each returned study drug tube.

Duration of Treatment:

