6.1.4 Adjustments for Covariates

Treatment group as factor and baseline values as covariate will be included in the primary and secondary endpoints analyses.

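### Vehicle is pooled across cohorts and application frequencies with no cohort term, so no planned table would show a cohort or vehicle-frequency effect

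*SAP*

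**What the plan says.** **Design.** The Protocol synopsis says: "Within each cohort subjects will be randomized in a 2:1 ratio to receive active or vehicle gel". SAP 4.1 gives 6 active and 3 vehicle per cohort and adds: "As soon as one cohort has been enrolled the next cohort will be recruited". SAP 4.1 also describes subjects as randomized to a cohort, but under this enrolment rule the time of entry decides the cohort.

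**Vehicle.** The synopsis lists once-daily vehicle and, as a separate item, "vehicle gel, applied topically, twice daily for 12 weeks". It also says: "Approximately 20 mg of gel will be applied to each tumor at each treatment". A vehicle-treated tumor thus receives about 20 mg of gel a day in Cohorts 1 and 2, and about 40 mg in Cohorts 3 and 4.

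**Analysis.** SAP 6.1 combines the vehicle groups: "For by treatment group summaries the vehicle gel group from each cohort will be combined into a single group". SAP 6.1.4 fixes the model: "Treatment group as factor and baseline values as covariate will be included in the primary and secondary endpoints analyses". SAP 6.7.1 and 6.7.2 add a t-test or Mann-Whitney test and Fisher's exact test, all unstratified. SAP 6.7.3 adds Cochran-Mantel-Haenszel (CMH) tests and names no strata. The pooling sentence speaks of summaries, but the table shells (for example Table 14.2.1.1) compute each regimen's p-value against a single vehicle column, so pooling reaches the tests. SAP 6.1.11 plans no subgroups, and SAP 8 gives no reason for pooling.

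**Aims.** SAP 2 says the trial is to establish a dose and regimen. The first primary objective in SAP 3 covers tolerability of vehicle applied once or twice daily.

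**The concern.** Randomization protects the active-versus-vehicle comparison inside a cohort. It does not protect a comparison of one cohort's active arm with vehicle subjects from other cohorts. If later subjects, samples or measurements differ from earlier ones, or if applying vehicle twice a day acts differently from once a day, the difference enters the regimen contrasts and can be read as an effect of strength or frequency. Direct comparisons between regimens carry the whole difference between their cohorts, and the SAP does not say that these are non-randomized.

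The planned tables would not reveal such a difference, because none shows cohort or vehicle frequency. The exposure table (Table 14.3.1.1) shows the consequence most plainly: one vehicle column would average two application schedules. The tolerability table (Table 14.3.1.2.1) pools in the same way, although once- and twice-daily vehicle are both named in a primary objective.

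**Working it through.** **Inputs.** Four cohorts of 6 active and 3 vehicle (SAP 4.1) give 4 × 9 = 36 subjects, 24 active and 12 vehicle. This agrees with the planned figure of about 36. The plan states no power, effect size or SD. Results below are therefore in residual SD units, with one tumor per subject, two-sided p<0.05 and no drug effect unless stated. All shift sizes are assumptions.

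**Bias against pooled vehicle.** The bias is the regimen's own cohort shift minus the mean shift over all vehicle subjects.

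- Cohort 4 alone shifts by d: 4% twice daily is biased by d − (3/12)d = 0.75d; every other regimen by −0.25d.
- Linear drift totalling D from Cohort 1 to Cohort 4 (0, D/3, 2D/3, D; mean D/2): end cohorts are biased by D/2 in absolute value, middle cohorts by D/6.
- Twice-daily cohorts differ from once-daily cohorts by f whatever the gel: twice-daily regimens are biased by f − (6/12)f = +f/2, once-daily regimens by −f/2. Comparing 4% with 2% at the same frequency is unaffected by f.
- Look after Cohort 3, if vehicle is pooled the same way (6 once daily, 3 twice daily): 2% twice daily is biased by f − (3/9)f = 2f/3. The look after Cohorts 1 and 2 has only once-daily vehicle and is frequency-matched.

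**How often p<0.05 would appear with no drug effect** (simulated two-sample t-test, 6 versus pooled vehicle):

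| Assumed pattern | 0.25 SD | 0.5 SD | 1.0 SD |
|---|---|---|---|
| Cohort 4 shift d, 4% twice daily | 6% | 10% | 25% |
| Linear drift D, end cohorts | – | 7% | 13% |
| Frequency effect f, any regimen | 5.5% | 7% | 12% |
| Frequency effect f, look after Cohort 3, 2% twice daily | 6% | 9% | 18% |

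Using the shared error of the five-group model changes the final-analysis rates by at most 3 percentage points (25% becomes 28%). With a cohort term the rate was about 5% in every pattern.

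**All patidegib versus vehicle.** At 6:3 in every cohort, each cohort makes up one quarter of both arms, so cohort shifts cancel and the bias is 0. The SE is √(1/24 + 1/12) = 0.354 SD with or without cohort. Residual df with baseline are 36 − 5 − 1 = 30 for five groups, and 36 − 4 − 1 − 1 = 30 for cohort plus active/vehicle. Cohort still helps precision: with an assumed 1-SD frequency shift and a 1-SD drug effect, power is about 78% with cohort and 71% for the unstratified t-test.

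Analysis by tumor and unimputed GLI1 results can disturb the 2:1 ratio. If 10–50% of subjects have two tumors and 0–30% of GLI1 results are missing at random (assumed), the share of a Cohort 4 shift entering by chance has a 95% range from about ±0.06d to ±0.18d for the ANCOVA contrast, and up to ±0.22d for the t-test. It is centred on zero.

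**Price of cohort adjustment for a single regimen.** The SE goes from √(1/6 + 1/12) = 0.500 to √(1/6 + 1/3) = 0.707 SD. The 95% half-width goes from 2.04 × 0.500 = 1.02 SD (30 df) to 2.05 × 0.707 = 1.45 SD (27 df).

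**Exposure column.** With full adherence over 12 × 7 = 84 days, six vehicle subjects have about 84 applications and six about 168. The mean is (84 + 168)/2 = 126 and the SD is 42 × √(12/11) ≈ 44, a summary that describes no subject.

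**The case against.** The strongest reply is that this is a small exploratory study. The SAP says: "P-values which are supplied are for descriptive purposes only". There is no alpha and no decision rule, so a reader who infers a broken error rate goes further than the documents allow. Pooling is a sensible choice for precision, as the half-widths above show. Several features limit any shift: cohorts follow directly on one another under the same eligibility criteria, there is one metasite, assessors are blinded and kept the same where possible, baseline is a covariate, and Protocol 8 calls the gel non-irritating. All of this stands, and it is why pooled vehicle should remain the main comparator for each regimen.

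Three other inferences are tempting and not supported.

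- That all-patidegib versus vehicle is biased. It is not systematically biased at 2:1. Even with 50% of subjects having two tumors and 30% of results missing, a Cohort 4 shift of 0.25, 0.5 or 1.0 SD gave p<0.05 in only about 4.7%, 4.8% and 3.7% of simulated two-group t-tests.
- That the CMH tests exclude cohort. SAP 6.7.3 leaves the strata unspecified.
- That the SAP promises a comparison of once- with twice-daily vehicle. SAP 5.1 says: "The efficacy endpoints are intended to compare once and twice daily application of 2% patidegib gel, 4% patidegib gel, and vehicle gel". This can equally mean comparing the patidegib regimens with vehicle. The firmer ground is the tolerability objective in SAP 3.

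Cohort data may also be seen at the unblinded looks (Protocol 7.3; SAP 4.1.3 and 6.1.6), and by-subject listings would let a reader rebuild cohort and frequency. This is a partial answer, since no by-cohort layout is specified. Finally, splitting vehicle gives 6 versus 6, which has 80% power only for a difference of about 1.8 SD. The split is for transparent description and would be a weak test.

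**Conclusion.** The point holds at minor to moderate weight. Each regimen-versus-pooled-vehicle contrast rests on 3 concurrent randomized controls out of 12 and would absorb 0.75 of a single-cohort shift or half of a vehicle-frequency effect. Shifts of 0.25 SD do little; shifts near 1 SD could mislead the choice of regimen. Which of these applies is unknown, because the documents give no size for either effect. The risk is a misread dose or frequency signal. For all-patidegib versus vehicle, a cohort term protects precision and guards against chance imbalance; it does not correct a systematic bias. Two findings need no assumption about shifts: no planned table shows vehicle by frequency, although both frequencies are in a primary objective, and the regimen-versus-regimen p-values compare cohorts that were not randomized against each other.

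**What to change.** 1. For all patidegib versus vehicle, use an ANCOVA with cohort, active/vehicle and baseline, and stratify the exact and CMH tests of that contrast by cohort. At 6:3 this costs nothing in SE or df. Under the unequal tumor counts assumed above, the SE is a median 0–1% higher than the five-group contrast (97.5th percentile up to 9%). A cohort with no evaluable vehicle tumor drops out of the adjusted contrast, and the SAP should say so.
2. Keep pooled vehicle as the main comparator for each regimen and give the reason. Show once-daily and twice-daily vehicle beside it in the efficacy, tolerability and exposure tables, including at the look after Cohort 3, and note that 6 versus 6 detects only large differences.
3. Label regimen-versus-regimen p-values as non-randomized comparisons across sequential cohorts.
4. Optionally, add the cohort-adjusted regimen-versus-vehicle contrast with its 95% interval as a sensitivity row, marked as low precision (half-width about 1.45 SD against 1.02 SD).

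The cost is SAP wording, two extra vehicle columns and at most one extra row. Trial conduct does not change.
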